#### **4.2.1.3 Non-parametric analysis of covariance**

A non-parametric ANCOVA model (Koch 1998) will be used for the endpoints that are not normally distributed, e.g. X-ray, MRI, et. ctrl. The macro NParCov3 will be used, see Zink and Koch 2012.

For continuous response variable, the macro call will be as follows:

```
%NParCov3(OUTCOMES = response, COVARS = weight baseline, C=1,
HYPOTH = ALT, STRATA = TNF $\alpha$  status, TRTGRPS = treatment, TRANSFORM = NONE,
COMBINE = FIRST, DSNIN = RESP, DSNOUT = OUTDAT);
```

Data set \_OUTDAT\_DEPTEST provides results for the treatment difference, and \_OUTDAT\_CI provides a 95% confidence interval for the treatment estimate.

For binary response variable, the macro call will be as follows:

```
%NParCov3(OUTCOMES = response, COVARS = weight, C = 1, HYPOTH = ALT, STRATA
= TNF $\alpha$  status, TRTGRPS = treatment, TRANSFORM = LOGISTIC,
COMBINE = FIRST, DSNIN = RESP, DSNOUT = OUTDAT);
```

The odds ratio and confidence interval are to be obtained from \_OUTDAT\_RATIOCI.

#### **4.2.2 Analysis of binary (and categorical) data**

##### **4.2.2.1 Analyses of Frequencies**

Summary statistics for discrete variables will be presented in contingency tables and will include count and frequency in each category. For n subjects, each at risk to experience a certain event with probability  $\pi$ , the crude incidence is estimated as  $p=x/n$ , where x is the number of subjects with the event.

If applicable, 95% confidence intervals for the relative frequencies will be derived as well based on the score method including continuity correction [Newcombe (1998)]:

With  $z$  as  $(1-\alpha/2)$ -quantile of the standard normal distribution (SAS:  $z=\text{PROBIT}(1-\alpha/2)$ ),  $n$  as total number of subjects (i.e. number of subjects in the denominator), and  $p$  as estimated crude incidence (number of subjects with event /  $n$ ) it is  $q=1-p$

Then the lower limit is

$$L = \max\left(0, \frac{2np + z^2 - 1 - z\sqrt{z^2 + 2 - \frac{1}{n} + 4p(nq+1)}}{2(n+z^2)}\right)$$

and the upper limit is

$$U = \min\left(1, \frac{2np + z^2 + 1 + z\sqrt{z^2 + 2 - \frac{1}{n} + 4p(nq-1)}}{2(n+z^2)}\right).$$

In addition, if  $L > p$  then  $L = p$  and if  $U < p$  then  $U = p$ .

For binary response variables (e.g. for ACR20/50/70, HAQ-DI responder, PASI 75, IGA response) the placebo-adjusted response rates including 95% confidence interval will be derived.

SAS code for risk difference:

```
Proc freq data=acr order=formatted;
```

```
Tables response*trt/ riskdiff;
```

```
Run;
```

(Note the response value should be sorted with '1' ahead of '0'.)

Fisher's exact test will be applied to rare events (e.g., MCR), pairwise treatment group comparisons to placebo or active controls.

SAS code for Fisher's exact test:

```
Proc freq data=mcr order=formatted;
```

```
Tables response*trt/Fisher;
```

```
Run;
```

If appropriate, an exact  $100*(1-\alpha)\%$  confidence interval (Clopper-Pearson 1934) will be obtained by using the SAS procedure PROC FREQ with the EXACT BINOMIAL statement. However, the confidence interval derived via the score method including continuity correction will be the default in safety analyses.

Figures will be provided for primary and secondary variables, with means and 95% confidence intervals displayed across time for all the treatment groups.

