While secukinumab 150 mg sc and 300 mg sc regimens are both more efficacious than placebo regardless of TNF α -inhibitor (TNF-IR) status, the 300 mg sc regimen provided the greatest efficacy across multiple PsA domains including ACR20, ACR50, ACR70, HAQ-DI, PASI 75, PASI 90, SF-36 PCS, and presence of dactylitis and enthesitis in TNF-IR patients.

Evidence of dose response was shown in TNF-IR patients favoring secukinumab 300 mg sc over 150 mg sc at the Week 24 efficacy endpoint used for the primary and secondary efficacy analyses of CAIN457F2312. Indeed, ACR20/50/70 response rates at Week 24 in TNF-IR patients were higher with secukinumab 300 mg sc compared to 150 mg sc (45.5% vs 29.7%, 27.3% vs 18.9% and 15.2% vs 10.8% respectively). This trend was maintained up to week 52.

Furthermore, secukinumab 300 mg sc was more efficacious than 150 mg sc in achieving clinically meaningful improvements in skin disease, particularly with respect to clear/almost clear skin (PASI 90, IGA mod 2011 0/1) in subjects with moderate to severe psoriasis (defined as $\geq 10\%$ BSA). There was a clear dose response favoring secukinumab 300 mg sc in the higher thresholds of skin clearance. The difference between 300 mg sc and 150 mg sc regimens was more pronounced in the more difficult-to-achieve PASI 90 and IGA mod 2011 0/1 endpoints, with 21.9% and 27.4% more patients with $\geq 10\%$ BSA compared to 8.2% and 3.3% more patients with $< 10\%$ BSA reaching PASI 90 and IGA mod 2011 0/1 responses, respectively, at Week 24. Therefore, secukinumab 300 mg sc afforded greater improvement in plaque psoriasis than 150 mg sc, particularly in the achievement of clear/almost clear skin, in subjects with moderate to severe psoriasis ($\geq 10\%$ BSA).

Thus, given the results outlined above, and in order to maintain a high proportion of clinically meaningful response without compromising the important Week 24 and Week 52 radiographic data integrity, the 150mg sc dose should be escalated to 300 mg sc every 4 weeks for subjects whose signs and symptoms are not well controlled, and may improve further with an increase in dose as judged by investigator beginning at Week 52. As treatment assignment will remain blinded until after the database is locked for the planned Week 52 interim analysis, for many subjects, both the decision to escalate and dose escalation will be performed in a blinded manner.

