5.3 Treatment assignment, randomization

At BSL, all eligible subjects will be randomized via Interactive Response Technology (IRT) to one of the five treatment arms as described in [Section 5.2](#). The investigator or his/her delegate will contact the IRT after confirming that the subject fulfills all the inclusion/exclusion criteria. The IRT will assign a randomization number to the subject, which will be used to link the subject to a treatment arm and will specify a unique medication number for the first package of investigational treatment to be dispensed to the subject. The randomization number will not be communicated to the site staff.

At Week 16, the investigator must contact the IRT in order to record the subject's responder status (responder/non-responder based on $\geq 20\%$ improvement in both swollen and tender joint counts) after the subject has been assessed. The IRT will not generate the medication number of PFSs to be administered at Week 16, if the subject's responder status is missing. After receiving the responder status IRT will assign the medication number of the PFS to be administered. IRT will only communicate to the caller the medication numbers.

The randomization numbers will be generated using the following procedure to ensure that treatment assignment is unbiased and concealed from subjects and investigator staff. A subject randomization list will be produced by the IRT provider using a validated system that automates the random assignment of subject numbers to randomization numbers. These randomization numbers are linked to the different treatment arms, which in turn are linked to medication numbers. A separate medication list will be produced by or under the responsibility of Novartis Drug Supply Management using a validated system that automates the random assignment of medication numbers to packs containing the investigational drug(s).

Subjects will be stratified at randomization on the basis of previous anti-TNF therapy as TNF-naïve or TNF-IR. Based on enrollment target, 70% of randomized subjects will be TNF-naïve and 30% TNF-IR to ensure a representative subject population for the assessment of efficacy and safety.

[figure not shown]
The randomization scheme for subjects will be reviewed and approved by a member of the Integrated Quantitative Sciences (IQS) Randomization Group.

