### **1.1 Study design**

This multicenter study uses a randomized, double-blind, placebo-controlled, parallel-group design. A screening period (SCR) running up to 10 weeks before randomization will be used to assess subject eligibility followed by 104 weeks of treatment.

At BSL approximately 990 subjects whose eligibility is confirmed will be randomized to one of four treatment groups in 2:2:2:3 ratio:

- Group 1 - secukinumab 150 mg s.c. without loading regimen
- Group 2 - secukinumab 150 mg s.c. with loading dose regimen
- Group 3 - secukinumab 300 mg s.c. with loading dose regimen
- Group 4 - Placebo s.c.

Subjects in Group 4 (Placebo) will be randomized (1:1) at BSL to two different treatment sequences:

Placebo s.c. till Week 16/24 followed by secukinumab 150 mg s.c. every 4 weeks starting at Week 16/24.

Placebo s.c. till Week 16/24 followed by secukinumab 300 mg s.c. every 4 weeks starting at Week 16/24.

**At randomization**, subjects will be stratified on the basis of previous anti-TNF therapy as TNF $\alpha$  inhibitor naïve (TNF-naïve) or TNF $\alpha$  inhibitor inadequate responders (TNF-IR).

At each study treatment visit, one (for secukinumab 150 mg) or two (for secukinumab 300 mg) s.c. injections in the form of PFS will be administered, since secukinumab is available in 1.0 mL (150 mg) PFSs. Placebo to secukinumab is also available in 1.0 mL to match the active drug.

**At Week 16**, subjects who have been randomized to secukinumab groups at BSL (Groups 1-3) will be classified as either responders ( $\geq 20\%$  improvement from BSL in both tender joint count (TJC) and swollen joint counts (SJC)) or non-responders ( $< 20\%$  improvement from BSL TJC or SJC), however, they will continue on the same treatment irrespective of their response status.

**At Week 16**, subjects who have been randomized to placebo at BSL (Group 4) will be classified as either responders ( $\geq 20\%$  improvement from BSL in both TJC and SJC) or non-responders ( $< 20\%$  improvement from BSL TJC or SJC):

- Subjects who are **non-responders** will receive either secukinumab 150 mg or 300 mg s.c. every 4 weeks starting at Week 16 (as dictated by treatment sequence assigned to these subjects at BSL).

- Subjects who are **responders** will continue to receive placebo every 4 weeks. At Week 24, these subjects will receive either secukinumab 150 mg s.c. or 300 mg s.c. every 4 weeks. (as dictated by treatment sequence assigned to these subjects at BSL).

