### **2.5.2 Statistical hypothesis, model, and method of analysis**

The statistical hypothesis for ACR20 being tested is that there is no difference in the proportion of subjects fulfilling the ACR20 criteria at Week 16 in the secukinumab regimens versus placebo regimen.

Let  $p_j$  denote the proportion of ACR20 responders at Week 16 for treatment regimens  $j$ ,  $j=0, 1, 2, 3$  where

- 0 corresponds to placebo regimen,
- 1 corresponds to secukinumab 300 mg,
- 2 corresponds to secukinumab 150 mg,
- 3 corresponds to secukinumab 150 mg no load,

In statistical terms,  $H_0: p_j = p_0$ ,  $H_{A_j}: p_j \neq p_0$ , for the  $j^{\text{th}}$  secukinumab regimen, i.e.

$H_1:$  secukinumab 300 mg is not different to placebo regimen with respect to signs and symptoms (ACR20 response) at Week 16

$H_2:$  secukinumab 150 mg is not different to placebo regimen with respect to signs and symptoms (ACR20 response) at Week 16

$H_3:$  secukinumab 150 mg no load is not different to placebo regimen with respect to signs and symptoms (ACR20 response) at Week 16

The primary endpoint of ACR20 at Week 16 in the FAS will be evaluated using a logistic regression with treatment and randomization stratum (TNF $\alpha$  status -naive or IR) as factors and weight as a covariate. Odds ratios will be computed for comparisons of secukinumab regimens versus placebo regimen utilizing the logistic regression model fitted.

The primary estimand of ACR20 response is the odds-ratio (each secukinumab dose vs. placebo) at week 16 in the FAS population that would be observed if all patients dropping out or being unblinded before week 16 or having with missing ACR20 data at week 16 were non-responders.

The overall testing strategy is explained in [Section 2.6.2.1](#).

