#### 4.2.2.2 Logistic regression

Certain binary outcome variables, e.g. response outcomes, will be evaluated using a logistic regression model with treatment regimen, weight, stratum if applicable. Odds ratios will be computed for comparisons of AIN457 regimens versus control(s) utilizing the logistic regression model fitted.

SAS code for logistic regression:

```
Proc logistic data=aaa;  
  Class TRT STRATA / param=glm;  
  Model AVAL = TRT WEIGHT STRATA;  
  Lsmeans TRT / diff cl exp;  
  Ods output diffs=lsm_diff;  
  Run;
```

Logistic regression will be applied to response variables at each visit.

In cases where logistic regression doesn't converge, Fisher's exact test will be applied for comparisons of between AIN457 doses. In this case, no odds ratios or confidence intervals will be estimated, but p-values may be calculated.

```
Proc freq data=aaa;  
  Table TRT * AVAL / fisher;  
  Where TRT in ("AIN457 xx mg" "Placebo");  
  Run;
```

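### The placebo-adjusted response rates leave out the TNF stratum and weight used by the adjusted test, so they do not correspond to its p-values and their 95% intervals are slightly wide if TNF status is prognostic

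*SAP*

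**What the plan says.** Randomisation uses prior anti-TNF exposure as its stratification factor (Protocol 5.3: "Subjects will be stratified at randomization on the basis of previous anti-TNF therapy"; SAP 1.1 says the same). The primary ACR20 endpoint "will be evaluated using a logistic regression with treatment and randomization stratum", with weight as a covariate, and the code in SAP 4.2.2.2 matches: "Model AVAL = TRT WEIGHT STRATA". ACR50, PASI75/90, enthesitis and dactylitis use the same model form (SAP 2.6.2.2). The MMRM and the non-parametric ANCOVA also carry the stratum and weight (SAP 4.2.1.2 and 4.2.1.3).

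The risk difference is the exception. SAP 4.2.2.1 gives ACR20/50/70, HAQ-DI response, PASI75 and IGA response as examples of endpoints for which "the placebo-adjusted response rates including 95% confidence interval will be derived". The code is "Tables response*trt/ riskdiff", with neither stratum nor weight. The visible SAP text has no stratified or adjusted risk difference. The binary call in SAP 4.2.1.3 does use the stratum, but it works on the logistic scale and returns an odds ratio.

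**The concern.** For each response endpoint the reader will see an absolute difference with an interval, and a p-value from another analysis. The p-value is adjusted for TNF stratum and weight; the difference is adjusted for neither.

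When randomisation is balanced within strata and the stratum predicts outcome, part of the response variation is explained by the stratum and does not contribute to the error of the difference. An unstratified variance still counts it, so the interval is too wide. TNF status looks prognostic in the sponsor's own data. In CAIN457F2312, "ACR20/50/70 response rates at Week 24 in TNF-IR patients were higher with secukinumab 300 mg sc compared to 150 mg sc", and the 150 mg ACR20 figure in TNF-IR subjects was 29.7% (Protocol, Amendment 1 rationale), against 51.0% for that dose overall (Protocol 3.3).

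The psoriasis subset raises a related issue. Skin involvement is not a stratification factor, so the TNF mix of subjects with at least 3% BSA is left to chance in each arm. The adjusted odds ratio allows for an imbalance there; the crude difference does not.

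At stake is how well the reported absolute effect matches the test beside it, and a small loss of precision.

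**Working it through.** **Inputs**
- ACR20 rates of 51% and 15%, with 220 and 330 subjects, at two-sided alpha 1.67% (SAP 3, Protocol 9.7).
- TNF split 70/30 (Protocol 5.3). Protocol 3.1 gives 154 TNF-naive of 220 and 231 of 330, which leaves 66 and 99 TNF-IR.
- Dropouts count as non-responders (SAP 2.5.3), so the denominators stay at 220 and 330.
- TNF-IR ACR20 rates of 29.7% (150 mg) and 45.5% (300 mg), from Protocol, Amendment 1 rationale. These are Week 24 results from CAIN457F2312; using them for Week 16 here is an assumption.
- Placebo ACR20 rate in TNF-IR: not in the documents. Assumed 5 to 20%, with the overall placebo rate held at 15%.

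**Step 1: the plan's own figure.** Exact Fisher power at these inputs is above 99.99%, consistent with the stated figure of over 99%. Under the same alpha, enthesitis gives 94.8% (stated: about 94%) and mTSS 83.3% (stated: 83%). The planning basis therefore reproduces. The documents state no interval width for the risk difference.

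**Step 2: unstratified interval.** SE = sqrt(p1·q1/n1 + p0·q0/n0) = sqrt(0.51·0.49/220 + 0.15·0.85/330) = sqrt(0.0011359 + 0.0003864) = 0.03902. Half-width = 1.96 × 0.03902 = 7.65 points, so 36.0 ± 7.65.

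**Step 3: TNF-stratified interval.** Mantel-Haenszel weights are proportional to n1h·n0h/(n1h + n0h), here 0.7 and 0.3. Var = Σ wh²·(p1h·q1h/n1h + p0h·q0h/n0h). The TNF-naive rates are solved so that the overall rates stay at 51% and 15%.

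Worked case, TNF-IR 29.7% on active and 15% on placebo:
- Active TNF-naive rate = (0.51 − 0.3·0.297)/0.7 = 0.601.
- Active term = (0.7·0.601·0.399 + 0.3·0.297·0.703)/220 = 0.0010475. The placebo term is unchanged at 0.0003864.
- SE = sqrt(0.0014339) = 0.03787, half-width 7.42 points.

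| TNF-IR active | TNF-IR placebo | Stratified half-width | Narrower by |
|---|---|---|---|
| 29.7% | 15% | 7.42 | 2.9% |
| 29.7% | 10% or 20% | 7.41 | 3.1% |
| 29.7% | 5% | 7.39 | 3.4% |
| 45.5% | 15% | 7.63 | 0.2% |
| 45.5% | 20% | 7.62 | 0.3% |
| 45.5% | 5% | 7.60 | 0.6% |
| 51% (no stratum effect) | 15% | 7.65 | 0% |
| 20% (extreme) | 2% | 7.10 | 7.1% |

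For the 45.5%/20% row, the active term is (0.7·0.5336·0.4664 + 0.3·0.455·0.545)/220 = 0.0011300 and the placebo term is (0.7·0.1286·0.8714 + 0.3·0.20·0.80)/330 = 0.0003831, so SE = 0.03890. The extreme row lies outside the rates in the documents and serves only as a bound.

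The point estimate is 36.0 points either way, because the strata are balanced.

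**Step 4: coverage.** In 200,000 simulated trials with TNF-IR at 29.7% on active and 5% on placebo, the unstratified 95% interval covered 95.6% and the stratified one 94.8%.

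**Step 5: psoriasis subset.** SAP 3 plans 110 against 165 subjects. If 30% were TNF-IR (an assumption), the standard deviation of the between-arm difference in TNF-IR share would be sqrt(0.3·0.7·(1/110 + 1/165)) = 5.6 points. Turning that into a shift in the PASI difference needs PASI rates by TNF status, which the documents do not give. For scale, the crude PASI75 half-width at 48% against 16% is 1.96 × sqrt(0.48·0.52/110 + 0.16·0.84/165) = 10.9 points.

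**The case against.** The strongest reply is that nothing in the plan rests on this number. SAP 2.5.2 says: "The primary estimand of ACR20 response is the odds-ratio (each secukinumab dose vs. placebo) at week 16 in the FAS population", obtained from the adjusted model, and SAP 2.6.2.2 names the odds ratio for the other binary secondary endpoints. The risk difference sits in an appendix section on frequencies. This stands. A reader might infer that the trial's headline effects carry inflated intervals, but the documents do not give the risk difference that standing.

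The effect is also small and in the safe direction, at most 0.26 points on a 36-point difference. A reader might take the upper end as the expected size. That relies on the lower of the two TNF-IR rates given in the same sentence; at 45.5% the narrowing is only 0.2 to 0.6%.

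On subsets, a reader might carry the ACR20 gap between TNF groups over to PASI, enthesitis or dactylitis and quote a shift in points. The documents give no rates by TNF status for those outcomes, and enthesitis and dactylitis are not among the examples in SAP 4.2.2.1. Nor is chance imbalance a bias: the crude interval's sampling error already includes it.

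A 95% interval need not agree with a test at 1.67% in any case. A difference stratified by TNF alone would still omit weight. Both points are correct, and the second favours the model-based fix.

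Finally, SAP 2.2.1 plans results by TNF status, and the text of SAP 2.5.4 (supportive analyses) is absent from this copy, so an adjusted difference may be specified there. Stratum-specific results do not supply an adjusted overall difference, so the mismatch in SAP 4.2.2.1 remains.

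**Conclusion.** The point holds as a minor one. The reported absolute differences are unadjusted while the test is adjusted for TNF stratum and weight, so the two do not correspond. For ACR20 at the planning rates the unstratified interval is mildly conservative: 7.65 points against 7.39 to 7.63. That range rests on the assumed 70/30 split, the earlier study's Week 24 TNF-IR rates and an assumed placebo TNF-IR rate of 5 to 20%. The gain vanishes if TNF status is not prognostic. The contribution of weight cannot be sized from the documents, nor can the effect of TNF imbalance on the PASI differences. The interval is not invalid, and no test, alpha level, sample size or decision changes.

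**What to change.** In SAP 4.2.2.1, derive each placebo-adjusted response rate by standardisation from the logistic model already fitted: predict every subject's response under each treatment, average over the analysis set (the psoriasis subset for PASI), take the difference, and give a delta-method 95% interval. Use the same TNF variable and weight as the model, so that the difference, odds ratio and p-value share one fit.

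If a simpler route is preferred, use a TNF-stratified Mantel-Haenszel difference, and state that weight is not in it. Keep the crude per-arm rates as descriptive.

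The cost is SAP wording and one procedure option (or a short post-processing step for standardisation). No new data are needed.

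A separate check belongs with the same edit. The code line puts response in rows, whereas the Fisher code in SAP 4.2.2.2 puts treatment in rows. If risks are read by row, the output at the planning rates would be 112.2/161.7 − 107.8/388.3 = 41.6 points, not the 36.0-point response difference.

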### **2.2.2 Treatment groups**

The summaries by treatment will be performed by the randomized treatment or treatment sequence. For some safety summaries (e.g. exposure-adjusted) the ‘switch’ treatment may be summarized separately.

- Randomized treatment:
  - AIN457 150 mg No Load
  - AIN457 150 mg
  - AIN457 300 mg
  - Placebo
- Treatment sequence:
  - AIN457 150 mg No Load
    - Stay with 150 mg
    - Up-titrated to 300 mg
  - AIN457 150 mg
    - Stay with 150 mg
    - Up-titrated to 300 mg
  - AIN457 300 mg
  - Placebo Non-responder – AIN457 150 mg
    - Stay with 150 mg
    - Up-titrated to 300 mg
  - Placebo Non-responder – AIN457 300 mg
  - Placebo Responder – AIN457 150 mg
    - Stay with 150 mg
    - Up-titrated to 300 mg
  - Placebo Responder – AIN457 300 mg

*Note:* up-titration subgroup analysis will be performed for the final Week 112 DBL only.

Up-titrated subgroup will include those subjects who are up-titrated to AIN457 300 mg in the second year. Additional sequences could be reported such as Any AIN457; Any AIN457 150 mg; Any AIN457 300 mg if applicable.

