## **3 Sample size calculation**

A 5% two-sided type I error rate will be used to control for type I error. Three secukinumab regimens will be tested versus placebo with respect to the primary endpoint (ACR20 response at Week 24), thus the type-I-error will be split to 1.67% two-sided for each comparison. Sample sizes will be based on this type I error assumption. With an assumed placebo rate of 15% and secukinumab 51% (FUTURE 2), the study is over 99% powered to detect a treatment difference of ACR20 in the FAS population, assuming 220 subjects in a secukinumab treatment group, and 330 subjects in the placebo group (Fisher's exact test, nQuery 7.0). This power is applicable for all three dose regimens, as the sample size is driven by structural endpoint.

Power for secondary variables was calculated using a two-sided 1.67% type I error. With an assumed placebo rate of 7% and secukinumab 35% (FUTURE 2), the study is over 99% powered to detect a treatment difference of ACR50 in the full FAS population, assuming 220 subjects in a secukinumab treatment group, and 330 subjects in the placebo group (Fisher's exact test, nQuery 7.0).

For structural endpoint, historical data (FUTURE 1) showed a standard deviation of 1.132 on active treatment and 2.435 on placebo at Week 24, and a difference of 0.52. Using the above assumptions, there is 83% power to show statistically significant differences assuming 220 subjects in a secukinumab group and 330 subjects in the placebo group (Satterthwaite t-test, nQuery 7.0).

A standard deviation of approximately 0.49 and a treatment difference of 0.17 has been observed for the change from baseline at Week 24 in HAQ-DI® (FUTURE 2). Using those assumptions, the study has approximately 94% power to detect a difference between secukinumab and placebo (Two group t-test, nQuery Advisor 7.0), assuming 220 subjects in a secukinumab treatment group and 330 subjects in the placebo group.

For the presence of dactylitis at Week 24 in the subset of subject who have dactylitis at BSL, with an assumed placebo rate of 85% and secukinumab 50% (FUTURE 2), there is about 99% power to show statistically significant difference between secukinumab (110) and placebo (165 subjects), assuming 50% subject have dactylitis at BSL (Fisher's exact test, nQuery 7.0).

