##### 4.2.4.2 Risk difference and 100\*(1- $\alpha$ )% confidence interval

For an investigational drug group with  $n_1$  subjects at risk, independent from the control group (e.g. placebo or comparator) with  $n_0$  subjects at risk, of whom  $x_1$  and  $x_0$  experience a certain event, the risk difference is estimated as  $p_1 - p_0$  with  $p_1 = x_1/n_1$  and  $p_0 = x_0/n_0$ .

Exact unconditional confidence limits for the risk difference will be obtained with SAS procedure PROC FREQ and option RISKDIFF in the TABLES statement, specifying the RISKDIFF option also in the EXACT statement.

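### The sample RISKDIFF code in SAP 4.2.2.1 has response as the row variable, so on an active-placebo pair it does not return the placebo-adjusted response rate

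*SAP*

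**What the plan says.** SAP 4.2.2.1 (Analyses of Frequencies) states that for binary response variables "the placebo-adjusted response rates including 95% confidence interval will be derived". Its examples are ACR20/50/70, HAQ-DI responder, PASI 75 and IGA response.

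The code given for the risk difference is a PROC FREQ step with formatted ordering and the request "Tables response*trt/ riskdiff". One note follows: response 1 should sort ahead of 0. There is no WHERE statement.

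Three other places in the SAP bear on this line:

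- Section 4.2.2.2 (Logistic regression) gives a Fisher fallback with treatment first, "Table TRT * AVAL / fisher", and a WHERE statement that limits the data to one AIN457 dose and placebo.
- Section 4.2.4.2 has its own formula, introduced with the words "experience a certain event, the risk difference is estimated as". It subtracts the control proportion from the investigational one, and each proportion is events divided by the subjects at risk in that group. The denominators are the treatment groups.
- Section 2.2.2 (Treatment groups) lists four randomized groups, with labels such as "AIN457 150 mg No Load" and Placebo.

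**The concern.** A placebo-adjusted response rate is the response rate on active minus the response rate on placebo, each with its own treatment group as denominator. In a PROC FREQ request A*B, A forms the rows, and RISKDIFF subtracts the row 2 proportion from the row 1 proportion in a 2x2 table. The SAP does not state this; it is ordinary software behaviour. With response in the rows, the denominators become responders and non-responders.

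Two things follow:

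1. If the dataset holds all four randomized groups, the call forms a 2x4 table and gives no active-placebo difference. A programmer must first restrict it to one pair.
2. If that restriction is the only change, the call returns P(active | responder) - P(active | non-responder).

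Sorting 1 ahead of 0 only decides which row comes first. With formatted ordering, AIN457 labels sort before Placebo, so the wrong value is positive and looks plausible.

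At stake are the crude absolute differences from placebo and their intervals for the listed binary responses. ACR20, the primary endpoint variable, is among them.

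**Working it through.** **Inputs.** All come from SAP section 3: ACR20 "With an assumed placebo rate of 15% and secukinumab 51% (FUTURE 2"); ACR50 7% and 35%; PASI75 16% and 48%; PASI90 9% and 33%. Group sizes are 220 active and 330 placebo for ACR, and 110 and 165 for PASI. These are planning values (the SAP ties the ACR20 calculation to Week 24) and serve here only as an illustration.

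**The plan's own figure.** Section 4.2.2.1 states no number to reproduce. The ACR20 power in section 3 (over 99%, Fisher's exact test, two-sided 1.67%) does reproduce: an exact enumeration gives more than 0.9999. This confirms the inputs.

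**Formulas.** Let a = pA·nA and c = pP·nP be the expected responders, b = nA - a and d = nP - c the non-responders.

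- Intended: a/nA - c/nP = (ad - bc)/(nA·nP)
- As coded, column 1 = active: a/(a+c) - b/(b+d) = (ad - bc)/[(a+c)(b+d)]
- Coded/intended = nA·nP/[(a+c)(b+d)] = t(1-t)/[r(1-r)], where t is the active share and r the pooled response rate
- Wald 95% limits: difference ± 1.96·√[q1(1-q1)/m1 + q2(1-q2)/m2], where q and m are the row proportions and row totals

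**As-coded values.**

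- ACR20: 112.2/161.7 - 107.8/388.3 = 0.694 - 0.278 = 0.416
- ACR50: 77.0/100.1 - 143.0/449.9 = 0.769 - 0.318 = 0.451
- PASI75: 52.8/79.2 - 57.2/195.8 = 0.667 - 0.292 = 0.375
- PASI90: 36.3/51.15 - 73.7/223.85 = 0.710 - 0.329 = 0.380

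| Endpoint | Intended, points (95% CI) | As coded, points (95% CI) | r | 0.24/[r(1-r)] |
|---|---|---|---|---|
| ACR20 | 36.0 (28.4 to 43.6) | 41.6 (33.2 to 50.0) | 0.294 | 1.16 |
| ACR50 | 28.0 (21.1 to 34.9) | 45.1 (35.8 to 54.4) | 0.182 | 1.61 |
| PASI75 | 32.0 (21.1 to 42.9) | 37.5 (25.3 to 49.6) | 0.288 | 1.17 |
| PASI90 | 24.0 (14.2 to 33.8) | 38.0 (24.2 to 51.9) | 0.186 | 1.59 |

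At 2:3 allocation t = 0.4, so t(1-t) = 0.24. For ACR50 the coded interval lies wholly above the intended one.

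**Could another part of the output be right?** For ACR20 the column 2 difference is 49.5/161.7 - 280.5/388.3 = 0.306 - 0.722 = -0.416. Neither column gives 0.360.

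**Dependence on allocation.** At 51% v 15% the intended difference is 36.0 points whatever the group sizes. The coded value is:

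- 220:330: 41.6
- 220:220: 112.2/145.2 - 107.8/294.8 = 0.773 - 0.366, or 40.7
- 220:110: 112.2/128.7 - 107.8/201.3 = 0.872 - 0.536, or 33.6

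**Direction.** The error is not always upward. At 220:330 with 60% v 30%, the coded value is 132/231 - 88/319 = 0.571 - 0.276, or 29.6 points instead of 30.0. When the two response rates are equal, both orientations give zero.

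**Fisher call.** The neighbouring request "Tables response*trt/Fisher" has the same orientation but does no harm, because the Fisher p-value does not change when the table is transposed. On 112/220 v 50/330 both orientations give 4.8 × 10⁻¹⁹.

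**The case against.** The strongest case against is about weight. The governing prose is clear, and the snippet looks like a template: its dataset names are placeholders, and nothing calls it production code. A wrong number needs a chain of events. Someone has to adapt the line, add only the two-arm restriction, keep the orientation despite the prose and the opposite snippet in 4.2.2.2, and then miss that the two tabulated rates do not subtract to the printed difference. The confirmatory analyses do not use the line at all.

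Several limits stand:

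- The 2x4 table is an assumption, since the SAP does not say what the dataset contains; it might already hold a single pair. The wrong difference on a pair follows either way.
- Section 4.2.4.2 concerns crude event incidence, so it supports the reading of a risk difference but does not define the efficacy quantity. The prose in 4.2.2.1 does that by itself.
- The figures are illustrative, and the size of the error in the trial cannot be predicted from them.
- No number stated in the SAP is wrong. The conflict is between prose and code.

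None of this rescues the line. It is the code the SAP supplies for a pre-specified efficacy output, and no output of that call on an active-placebo pair is the intended difference. Copying the WHERE statement from 4.2.2.2 is the obvious adaptation, and it yields a plausible wrong number. That the error could be noticed later is no reason to leave it in the plan.

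**Conclusion.** The concern holds. As printed, the line conditions on response instead of treatment, contrary to the sentence it is meant to implement. Under the SAP's planning rates the printed differences would be 1.16 to 1.61 times the intended ones, with correspondingly wrong intervals; at other rates or allocations the error can be small or go the other way. No figure is claimed for HAQ-DI or IGA response, because the SAP gives no planning rates for them.

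The conclusion rests on standard PROC FREQ row and RISKDIFF conventions and on the line being run on one active-placebo pair. The sign shown also assumes that AIN457 labels sort ahead of Placebo.

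The error is confined to the crude differences and their intervals. The logistic-regression odds ratios, which are the primary estimand for ACR20 (SAP 2.5.2), are untouched, as are the tests, alpha control, power and sample size. It should be corrected, but it does not threaten the confirmatory results.

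**What to change.** In SAP 4.2.2.1 replace the table request with `tables trt*response / riskdiff;`. Run it separately for each active-placebo pair, with a WHERE statement restricting to the two arms as in 4.2.2.2. State that the active regimen is row 1 and response=1 is column 1. Add a program check that each printed difference equals the two tabulated response rates subtracted.

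The cost is one corrected line, one added line and the check. Data, endpoints and tests do not change.
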